	The outcome will be determined by the modified pouchitis disease activity index (mPDAI) and the need for antibiotic therapy to control symptoms. The mPDAI is a composite index consisting of 2 disease variables (clinical criteria of pouchitis: number of bowel movements, blood in stool, urgency and fever with a maximum score of 6 and endoscopy criteria of pouch inflammation with a maximum score of 6. The maximum combined score is 12).	
	 Complete remission is defined as a mPDAI score = 0 and no need for antibiotics. Clinical remission is defined as a clinical mPDAI score ≤ 4 and no need for antibiotics. Symptomatic improvement is defined as a decrease from baseline in the mPDAI clinical subscore of 2 points and no need for antibiotics. Symptomatic worsening of the disease is defined by an increase in the mPDAI clinical subscore of 2 points or the need for antibiotics. 	
	The severity of the pouch inflammation will be evaluated by two pouchoscopies (week 0 and week 4). Endoscopic improvement is defined as a decrease from baseline in the mPDAI endoscopic subscore of 2 points.	
Primary variables	Safety and tolerability of endoscopically and orally applied FMT	
Secondary variables:	 Clinical remission (mPDAI score ≤4 points) and no need for antibiotic therapy at week 4. Clinical remission (clinical mPDAI score ≤ 4) and no need for antibiotics at week 8*. Clinical remission (clinical mPDAI score ≤ 4) and no need for antibiotics at week 16*. Endoscopic improvement of active pouchitis (decrease from baseline in mPDAI endoscopic subscore ≥ 2 points) at week 4. 	

	 Response: Symptomatic improvement of active pouchitis (decrease from baseline in mPDAI clinical subscore ≥ 2 points) and no need for antibiotic therapy at week 4. Response: Symptomatic improvement of active pouchitis (decrease from baseline in mPDAI clinical subscore ≥ 2 points) and no need for antibiotic therapy at week 8*. Response: Symptomatic improvement of active pouchitis (decrease from baseline in mPDAI clinical subscore ≥ 2 points) and no need for antibiotic therapy at week 8*. Response: Symptomatic improvement of active pouchitis (decrease from baseline in mPDAI clinical subscore ≥ 2 points) and no need for antibiotic therapy at week 16*. 	
	*Only patients who do not continue in open label extension	
	• Exploratory analyses (OL=Open label):	
	 Endoscopic improvement of active pouchitis (decrease from baseline in mPDAI endoscopic subscore ≥ 2 points) at in open label extension week 8. 	

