	 Clinical remission (mPDAI score ≤4 points and a decrease in the baseline mPDAI> 2 points) and no need for antibiotic therapy at week 10 OL. 	
	 Clinical remission (clinical mPDAI score ≤ 4) and no need for antibiotics at week 14 OL. 	
	 Clinical remission (clinical mPDAI score ≤ 4) and no need for antibiotics at week 22 OL. 	
	• Response: Symptomatic improvement of active pouchitis (decrease from baseline in mPDAI clinical subscore ≥ 2 points) and no need for antibiotic therapy at week 10 OL.	
	 Response: Symptomatic improvement of active pouchitis (decrease from baseline in mPDAI clinical subscore ≥ 2 points) and no need for antibiotic therapy at week 14 OL. 	
	 Response: Symptomatic improvement of active pouchitis (decrease from baseline in mPDAI clinical subscore ≥ 2 points) and no need for antibiotic therapy at week 22 OL. 	
	 Symptomatic worsening of active pouchitis (decrease from baseline in mPDAI clinical subscore ≥ 2 points) from FMT week 0 – week 16 Quantitative changes in mPDAI from baseline values 	
	 Quantitative changes of calprotectin from baseline 	
	Alterations in stool microbiome after FMT	
	Engraftment of donor FMT	
Statistical analysis:	Remission and response as defined by mPDAI scores will be analysed by intention-to-treat design. Wilcoxon rank sum tests will be carried out to assess differences in the pre- and post-treatment mPDAI total scores and subscores. P values < 0.05 will be considered to be statistically significant.	
Duration of study	2 weeks of FMT/ placebo therapy followed by evaluation of clinical and endoscopic outcome at week 4, and clinical evaluation at week 8 and 16. In case the study patients does not achieve clinical remission at week 4 or	

	experiences a flare of disease on day 15-28 after start of the study he/she will be offered the possibility to participate in open label extension with an additional endoscopic FMT followed by 2 weeks of oral FMT and clinical follow up at week 10, 14 and 22.
	The anticipated time of the overall study is 18 months
Number of centres:	Single center study

2. BACKGROUND:

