If the patient is not willing to continue in the open label part of the study, he/she will be followed in the regular arm with visits 6-9.

Study visits for patients at remission at phone visit 4 and site visit 5

Phone visit 6 will evaluate for adverse events and review the adverse event diary. At this point (4 weeks after stopping the oral FMT) the patient can stop filling out the daily adverse event diary. However, the patient will be reminded to bring the completed adverse event diary to site visit 7. Additionally, the mPDAI will be calculated and the concomitant medications will be assessed.

Site visit 7 will collect all pages of the adverse event diary, and review the adverse events, which occurred since visit 6. A physical exam and blood tests will be performed and the mPDAI will be calculated. The concomitant medications will be assessed. A stool sample will be collected from the patient.

Site visit 8 will review new adverse events, concomitant medications and the mPDAI score. A stool sample will be collected from the patient.

On the last phone visit 9 the coordinator will review serious adverse events only, which may have occurred since visit 8.

Open label extension period

After at least 10 days of antibiotic therapy a pouchoscopy and FMT will be performed at site visit 6OL. A physical exam will be completed, adverse events and concomitant medications reviewed. Female patients will provide a urine sample for a pregnancy test before FMT. Similar to the previous FMT the study patient will be started on omeprazole 20 mg (1 tablet/daily) as long as he/she undergoes oral FMT therapy.

In phone visit 7OL the coordinator will ask the study patient if adverse events occurred, review the adverse event diary, and will evaluate the clinical components of the mPDAI of the last 3 days before the phone call (stool frequency, rectal bleeding, fecal urgency/ abdominal cramping, fever) as well as the concomitant medications.

At site visit 8OL the study coordinator will ask the study patient if adverse events occurred, review the adverse event diary, and will evaluate the clinical components of the mPDAI of the last 3 days before the visit (stool frequency, rectal bleeding, fecal urgency/ abdominal cramping, fever) as well as review the concomitant medications. The coordinator will collect the stool sample from the patient, which should be collected 1-3 days after the end of the oral FMT therapy .

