Calculation of mPDAI score (before pouchoscopy)

Pouchoscopy (in patients in clinical remission and no need for antibiotics only): Evaluation of endoscopic PDAI.

If patient is in clinical remission (mPDAI ≤ 4) and no need for antibiotics proceed to pouchoscopy

If patient is not in clinical remission (mPDAI > 4) or need for antibiotics or comes in due to exacerbation of symptoms with possibility to continue with open label extension. Need to restart 10 day course of antibiotics as standard of care similar to initial antibiotic treatment before the first FMT

In case of **premature withdrawal** from the study (yes, no)

If yes, reason:

- Intolerance of medication
- Lack of efficacy (need for steroids e.g. increase of steroids or re-introduction of steroids after previously successful taper)
- Severe adverse event
- Lack of patient's cooperation
- Inclusion criterion not fulfilled or exclusion criterion fulfilled coming to knowledge after recruitment
- Other reason

9. FOLLOW-UP VISITS OF PATIENTS IN REMISSION AT WEEK 4 OR NOT PARTICPATING IN THE OPEN LABEL EXTENSION

• Visit 6: Phone visit week 6 (42 +/- 3 days after first transplant)

Formal aspects:

Adverse events (review adverse events diary, last day of filling out the diary is 28 days after end of oral FMT, which is around week 6; patient needs to be advised to bring filled out diaries to visit 7)

Concomitant medication

Calculation of clinical mPDAI (stool frequency, rectal bleeding, fecal urgency/abdominal cramping, fever)

• Visit 7: Site visit week 8 (56 +/- 5 days after first transplant)

Examinations

Vital signs: blood pressure (mm Hg), heart rate (min-1), weight (kg), temperature

Physical examination:

- Head (including ENT and eyes)
- Lymphatic system
- Endocrine system
- Lungs and respiratory tract
- Peripheral vascular system
- Cardiovascular system

- Gastrointestinal tract, liver, spleen
- Urogenital system
- Nervous system
- Muscular and skeletal system
- Skin and connective tissue
- Other

each: actual status: Present finding / normal condition / not examined

Measurement of laboratory parameters

Hematology Serum chemistry

Stool collection: Bring to clinic.

Formal aspects:

Concomitant medication

Adverse events (adverse events diary filled out until visit 6)

Calculation of mPDAI score

Reminder stool collection and bring in stool week 16.

Collect adverse event diary (filled out until week 6)

• Visit 8: Site visit week 16 (112 +/- 7 days after first transplant)

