16. WITHDRAWAL CRITERIA

• Criteria in individual cases

Any study patient can withdraw from the study at any time without personal disadvantages and without having to give a reason. The time of withdrawal, the results available up to that time, and, if known, the reason for withdrawal must be documented on the CRF.

The investigator can also discontinue the study after considering the risk-to-benefit ratio, if he/she no longer considers the further participation of the study patient justifiable. The date of and the primary reason for the withdrawal as well as the observations available at the time of withdrawal are to be documented on the CRF.

Reasons leading to the withdrawal of a study patient can include the following (primary reason must be determined):

- Development of a SAE that is thought to be likely secondary to study drug or study intervention.
- Development of an AE with ≥ grade 3 toxicity, using the FDA toxicity grading scale for preventive vaccines (

If the PI or DSMB believes it is no longer in the subject's best interest to continue participation in the study. Examples include:

- A serious or unexpected adverse event
- Serious inter-current illness, or
- Progression of disease that requires alternative treatment.
- The subject no longer meets the inclusion criteria.
- Lack of compliance with study procedures or study treatment, as determined by the PI.

In all study patients who finish the study prematurely, a withdrawal examination should be carried out within 3 weeks after the last application of the study medication. The withdrawal examination must be conducted as a final examination and documented in the CRF. It is most important to calculate at least the final mPDAI score for each study patient. If possible, an endoscopy with biopsies according to the protocol should be performed and blood samples for hematology and serum chemistry should be taken.

The investigator will continue to observe study patients withdrawn from the study because of intolerable AEs until the findings have been clarified.

• Criteria for the termination of the whole study

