- Response: Symptomatic improvement of active pouchitis (decrease from baseline in mPDAI clinical subscore ≥ 2 points) and no need for antibiotic therapy at week 4.
- Response: Symptomatic improvement of active pouchitis (decrease from baseline in mPDAI clinical subscore ≥ 2 points) and no need for antibiotic therapy at week 8*.
- Response: Symptomatic improvement of active pouchitis (decrease from baseline in mPDAI clinical subscore ≥ 2 points) and no need for antibiotic therapy at week 16*.

*Only patients who do not continue in open label extension

- Exploratory analyses (OL=Open label):
- Endoscopic improvement of active pouchitis (decrease from baseline in mPDAI endoscopic subscore ≥ 2 points) at in open label extension week 8.

- Clinical remission (mPDAI score ≤4 points and a decrease in the baseline mPDAI> 2 points) and no need for antibiotic therapy at week 10 OL.
- Clinical remission (clinical mPDAI score ≤ 4) and no need for antibiotics at week 14 OL.
- Clinical remission (clinical mPDAI score ≤ 4) and no need for antibiotics at week 22 OL.
- Response: Symptomatic improvement of active pouchitis (decrease from baseline in mPDAI clinical subscore ≥ 2 points) and no need for antibiotic therapy at week 10 OL.
- Response: Symptomatic improvement of active pouchitis (decrease from baseline in mPDAI clinical subscore ≥ 2 points) and no need for antibiotic therapy at week 14 OL.
- Response: Symptomatic improvement of active pouchitis (decrease from baseline in mPDAI clinical subscore ≥ 2 points) and no need for antibiotic therapy at week 22 OL.
- Symptomatic worsening of active pouchitis (decrease from baseline in mPDAI clinical subscore ≥ 2 points) from FMT week 0 week 16
- Quantitative changes in mPDAI from baseline values
- Quantitative changes of calprotectin from baseline
- Alterations in stool microbiome after FMT
- Engraftment of donor FMT

Clinical analyses

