The primary endpoint is the evaluation of safety and tolerability of FMT in patients with ADP. Secondary endpoints are endoscopic and clinical remission at week 4 in conjunction with no need for antibiotic therapy, clinical response and remission and no need for antibiotics at week 4,8 and 16, endoscopic improvement of pouchitis and quantitative changes of calprotectin after the initial FMT. All subjects with missing data for determination of endpoint status will be considered as a non-responder in the intention-to-treat analysis. For dichotomous outcomes we will compute the percentage of subjects having the event along with a 95% confidence interval. For continuous outcomes we will compute the mean and a 95% confidence interval for the mean as well as descriptive statistics such as median, range and upper and lower quartiles. In addition to computing these measures for all 20 subjects, we will compute them for subgroups of interest (e.g. endoscopic active vs inactive ADP). These estimates can then be used in the planning of a larger, hypothesis-based study.

• Sample size calculation

This trial is designed as a proof-of-concept study of FMT therapy, not a definitive evaluation of FMT therapy in patients with ADP. The goal is to evaluate the safety and feasibility of such a trial, as well as to estimate the effect sizes in placebo and FMT therapy groups in order to accurately estimate the sample size needed for subsequent evaluation in a larger definitive trial. Nonetheless, we estimated the minimum effect size this pilot study can detect. We assume a placebo remission rate (defined as clinical remission and no need for antibiotics) of 10%. The low placebo response rate is based on the inclusion criterion, which selects only patients needing continuous or recurrent antibiotic therapy in the setting of ADP. With a follow-up of 16 weeks with the requirement of clinical remission without antibiotic therapy at end of follow-up, a placebo response rate beyond 10% is highly unlikely. The recent case series of Stallmach et al. suggests an antibiotic-free remission rate of 80% and a response rate of 100% in the setting of repeated FMT.⁴⁹ With 20 patients (1:1 randomization), and a placebo response rate of 10%, we will have 80% power to detect an effect difference of 67.5%, that is, an antibiotic-free remission rate

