Distribute/Review Subject adverse events diary ^b			Х	X	X	X	Х

Study visits Chart for patients continuing in observation phase

Visit	6	7	8	9	Early termination ^g
Type of visit	Phone	Site	Site	Phone	Phone/site
Day	42	56	112	168	
	+/-3	+/-5	+/-7	+/-10	
Week	6	8	16	24	
mPDAI score	Х	X ^d	X ^d		Х
Concomitant Medication	Х	Х	X		Х
Adverse Events	Х	Х	X	X ^I	Х
Physical Exam		Х			Х
Blood Tests ^a		Х			Х
Stool sample		Xf	Xf		
Sigmoidoscopy (Pouchoscopy					
Distribute/Review Subject Diaries ^b	Х	Х			Х
Distribute/Review Subject adverse events diary ^b	Х	Xj			X

1.2 STUDY VISITS CHART OPEN LABEL EXTENSION FOR PATIENTS WITH RESPONSE ONLY OR NO RESPONSE OR EARLY TERMINATION DUE TO FLARE IN PLACEBO-CONTROLLED TRIAL SECTION

Visit	60L	70L	80L	90L	100L	110L	120L	130L	Early termination ^g
Type of visit	Site	Phone	Site	Site	Phone	Site	Site	Phone	Phone/site
Day (post 2nd transplant)	38 (0)	46 (8)	53 (15)	66 (28)	80 (42)	94 (56)	150 (112)	206 (168)	
38 (0)	38 (0)	+/-1	+3	+/-3	+/-3	+/-5	+/-7	+/-10	
Week (post 2nd transplant)	6 (0)	7 (1)	8 (2)	10 (4)	12 (6)	14 (8)	22 (16)	30 (24)	
mPDAI score		X ^d	X ^d	Х	Х	X ^d	X ^d		Х
Concomitant Medication	Х	Х	Х	Х	Х	Х	Х		Х
Adverse Events	Х	Х	Х	Х	Х	Х	Х	XI	Х
Physical Exam	Х			Х		Х			Х
Blood Tests				Х		Х			Х
Pregnacy test (urine)	Х								
Dispense FMT capsules + omeprazole	X ^g								
Stool sample			Xf	Xf		Xf	Xf		Х
Sigmoidoscopy (Pouchoscopy	Х			Х					
Endoscopic FMT	X ^h								
Distribute/Review Subject PDAI Diary ^b	Х	Х	Х	Х	Х	Х	Х		X
Distribute/Review Subject adverse events diary ^b	Х	Х	Х	Х	Х	Xj			X

^a Pouchoscopy visit 5 only in patients who are in remission (mPDAI<4) as assessed in visit 4 by phone or in patients with clinical active pouchitis, but not willing to participate in open label extension

^b There will be two subject diaries provided to the patient: One for the evaluation of the mPDAI will be provided at Screening. The study patient will complete this diary each day, beginning with the Screening visit, and ending with the Week 16 visit. Stool frequency, rectal bleeding, fecal urgency or abdominal cramps, and/or fever will be recorded. A minimum of three days of diary entries will be required during the week prior to randomization, Phone visit week 1 and 2 and Visit Week 4 and 8. The last three days of diary entries will be used to calculate stool frequency and fecal urgency/abdominal pain scores and clinical mPDAI subscores.

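### Week-4 total mPDAI and endoscopic subscore are measured mainly in patients who did well, so their planned tests and mean changes look more favourable than the randomised group

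*Combined protocol and SAP*

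**What the plan says.** All references are to the combined protocol and SAP.

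- **Tests and summaries.** Section 1 (Statistical analysis) states that "Wilcoxon rank sum tests will be carried out to assess differences in the pre- and post-treatment mPDAI total scores and subscores". Section 20 lists "Quantitative changes in mPDAI from baseline values" among the exploratory analyses. Its Clinical analyses paragraph promises a mean with 95% CI for continuous outcomes, computed for all 20 subjects.
- **Who is scoped at week 4.** Section 8, Visit 5: "Pouchoscopy (in patients in clinical remission and no need for antibiotics only): Evaluation of endoscopic PDAI". Footnote a to the section 21 visit charts widens this to remitters "or in patients with clinical active pouchitis, but not willing to participate in open label extension". Section 1 gives no restriction: "The severity of the pouch inflammation will be evaluated by two pouchoscopies (week 0 and week 4", with no mention of remission status. The section 11 heading lists screening, visit 5 or visit 6OL.
- **Patients who enter the extension.** Section 7: "After at least 10 days of antibiotic therapy a pouchoscopy and FMT will be performed at site visit 6OL".
- **Patients who withdraw.** Section 16: "If possible, an endoscopy with biopsies according to the protocol should be performed".
- **Missing data.** Section 20, Clinical analyses: "All subjects with missing data for determination of endpoint status will be considered as a non-responder in the intention-to-treat analysis". No other rule is given.

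**The concern.** Whether a week-4 total or endoscopic score exists depends on the outcome being measured. A patient who flares and enters the extension has no off-antibiotic week-4 pouchoscopy. The non-responder rule settles a yes/no status for that patient but cannot supply a number of points. As written, a pre/post test or mean change for these two scores uses the patients who happen to have been scoped, although the text speaks of all 20.

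The stake is the trial's stated purpose. Section 20 says the estimates can be used to plan a larger study. A change in total mPDAI taken from remitters, read as a whole-group result, would carry an over-favourable figure into that planning.

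**Working it through.** **1. The plan's own figure.** The documents give no figure for the score tests, so the check starts from the sample-size statement: 10 per arm, 10% v 77.5%, two-sided 0.05, Fisher's exact test. Power = sum over x, y = 0..10 of Bin(x; 10, 0.10) × Bin(y; 10, 0.775) × [Fisher p < 0.05] = 0.8016. This reproduces the stated 80%.

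**2. How many patients have a week-4 score.**
- Expected remitters: 10 × 0.10 = 1.0 on placebo and 10 × 0.775 = 7.75 on FMT, together 8.75. Section 20 (Microbiome Analyses) assumes 9 in remission and 11 in the extension, which agrees.
- If every non-remitter enters the extension, 20 - 8.75 = 11.25 lack the score: 9.0 on placebo and 2.25 on FMT.
- P(at most one placebo remitter) = 0.9^10 + 10 × 0.1 × 0.9^9 = 0.349 + 0.387 = 0.736.
- Caveat: the 10% placebo rate is argued from a 16-week requirement, so more patients could be in remission at week 4.

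**3. What each kind of patient contributes.**

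| Patient at week 4 | Off-antibiotic week-4 pouchoscopy | Score from the missing-data rule |
|---|---|---|
| Remission, no antibiotics | Yes | Not needed |
| Active, declines extension | Yes by footnote a; no by the Visit 5 text | None |
| Active, enters extension | No; next scope at 6OL after antibiotics | None |
| Withdrawn | Only if possible | None |

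**4. Size of the selection effect if nothing changes.** Let D be the post minus pre total score. In all patients E[D] = 0; in scoped patients the quantity estimated is E[D | week-4 clinical subscore ≤ 4].

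Assumptions not in the documents: normal scores rounded and held to 0-6; SD 1.3 (clinical) and 1.5 (endoscopic); endoscopic mean 3; the same distribution at both times. The clinical mean is set to 4.7, so that the share scoped is Φ((4.5 - 4.7)/1.3) = Φ(-0.154) = 0.44, matching about 9 of 20.

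| Pre/post correlation | Clinical/endoscopic correlation | Total change, scoped | Endoscopic change, scoped | Falsely significant improvement (signed-rank, 1,000 trials) |
|---|---|---|---|---|
| 0.3 | 0 | -0.83 | -0.01 | 15.2% |
| 0.3 | 0.3 | -1.10 | -0.27 | 20.3% |
| 0.3 | 0.6 | -1.38 | -0.56 | 25.8% |
| 0.6 | 0 | -0.51 | 0.00 | 11.1% |
| 0.6 | 0.3 | -0.67 | -0.16 | 13.6% |
| 0.6 | 0.6 | -0.83 | -0.32 | 15.5% |

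The nominal rate in that direction is 2.5%. With all 20 scored, it was 1.5-2.9% for the total score and 1.9-2.6% for the clinical subscore.

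**5. Dependence on the share scoped.** Still with no group change:
- Clinical mean 4 (65% scoped): total change -0.34 to -0.88.
- Clinical mean 3 (87-88% scoped): -0.14 to -0.36.
- Clinical mean 2 (97% scoped): -0.04 to -0.09.
- Scoping decliners also helps. At correlations 0.5 and 0.4 the change is -0.88 with no non-remitter scoped, -0.51 with 25% scoped and -0.26 with 50%.

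**6. An antibiotic-treated baseline.** Section 7 has all patients on antibiotics for at least 10 days before week 0, stopped 24 hours before FMT. Section 19 takes the baseline symptoms from the three diary days before week 0. Using the model of step 4 with both correlations at 0.6 and a low baseline that then worsens:

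| Mean clinical/endoscopic, baseline → week 4 | Change, all 20 | Change, scoped | Difference |
|---|---|---|---|
| 2/2 → 4.7/3 | +3.51 | +2.71 | 0.80 |
| 2/2 → 4.7/2 | +2.58 | +1.81 | 0.77 |
| 3/2.5 → 4.7/3 | +2.07 | +1.32 | 0.75 |
| 4/3 → 4.7/3 | +0.63 | -0.15 | 0.78 |

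The scoped patients look better by about 0.75 to 0.80 points in every row, but the sign of the observed change depends on the baseline.

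**The case against.** **A reader might infer that the planned tests will show improvement even when nothing has changed.** The documents do not support that. It needs a group that is unchanged and yet mostly above the clinical cut-off at both times. Baseline is taken on antibiotics, and one inclusion route is remission maintained on antibiotics. If 11 of 20 relapse from there, the group has worsened. A separate simulation from such a baseline, with about 9 scoped, gave an observed change of +1.6 to +2.5 against a true +2.6 to +3.5, with no false improvements. The cut-off is also lenient (4 of 6), and at a low unchanged clinical mean nearly everyone passes it. The 9/11 split comes from a stool-sample count and also reflects need for antibiotics, which need not follow the clinical score. All of this stands.

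**A reader might also infer that a planned comparison of scores between arms has no power.** With 8 FMT scores and 1 placebo score, the smallest exact two-sided rank-sum p is 2/9 = 0.22, so a complete-case comparison would indeed be uninformative. But section 1 describes pre/post differences; no between-arm score test is stated.

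**The consequence is limited.** The primary endpoint is safety, the study is proof of concept, the change in mPDAI is exploratory, and the Wilcoxon sentence appears only in the summary. Section 1 can be read as scoping everyone at week 4, so part of this is an inconsistency. That also stands.

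What survives is the direction: in every scenario tried, scoped patients looked better than the full group, negligibly so when nearly all are scoped. The plan has no rule for the rest.

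**Conclusion.** The point holds in a limited form. For total mPDAI and the endoscopic subscore at week 4, the planned tests and mean changes rest on patients selected by outcome: about 9 of 20 at the plan's rates, about one on placebo, if few non-remitters decline the extension. The result is biased toward looking better. Whether that creates a false improvement or only understates a worsening depends on the baseline state, which the documents do not quantify.

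Under the stated assumptions, with no group change and about 44% scoped, the spurious total change is roughly -0.5 to -1.4 points; it approaches zero as the share scoped approaches 100%. The false-significance rates in the working are conditional on that same no-change scenario and are not predictions for this trial.

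This should be corrected before analysis, but it does not threaten the trial's main conclusion on safety.

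**What to change.** 1. **Reconcile who has a week-4 pouchoscopy.** Section 1, section 8 (Visit 5), the section 11 heading and footnote a in section 21 disagree. The cut-off differs too: ≤4 at Visit 5, <4 in the footnote.
2. **Compare arms in all 20 randomised patients.** For week-4 total mPDAI and endoscopic subscore, use a two-sample Wilcoxon test. Give the tied worst rank to patients who relapsed, restarted antibiotics or entered the extension without an off-antibiotic week-4 pouchoscopy.
3. **Report change among scoped patients as description only**, with the number scoped per arm and no p-value.
4. **Do not use the 6OL pouchoscopy as the post-treatment value**; it follows at least 10 days of antibiotics.
5. **For change in points, use the clinical subscore** from the last diary days before any antibiotic restart: visit 4 or the flare contact, otherwise visit 5. State the timing for each patient. Visit 5 alone will not do, because section 7 lets non-remitters restart antibiotics after phone visit 4, with visit 5 planned 3-4 days later. Early termination can fall on any of days 1-28.

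Cost: SAP wording, plus the protocol reconciliation in item 1; the analysis needs no new data or procedure. The downside is that the worst-rank result is a rank comparison rather than a mean change, and it partly repeats remission status.
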